Patients will be randomized 1:1 into two different treatment groups using a block randomization scheme. Using the Proc Plan procedure within SAS 9.4 (SAS Institute, Carey NC), blocks will be constructed based on surgeon and patient gender. Each surgeon will have a randomization list generated, and patient assignment will be made after the informed consent process has been performed to the next assignment on the list. Randomization assignments will not be revealed to the study personnel until after the patient has been enrolled in the study so as not to unduly bias the consent process.

Blinded evaluators will be used to calculate the primary outcome variable of interest, estimated blood loss per level fused. All other study personnel, including the surgeons, will not be blinded to participant treatment assignment which is necessary to ensure the correct protocol is followed. Patients and their families will be blinded to study assignment to minimize the risk of assignment related study withdrawal. Patients and their families will not have the assignment revealed to them after the surgery as it will not affect their plan of care. If desired, treatment allocation may be revealed at the final study visit at one year following surgery.

e. Intraoperative Estimated Blood Loss

Estimated blood loss will be determined by 3 different methods. The first and primary method is to use the estimated blood loss listed on the cell saver report. This measurement is generated by the cell saver based on the blood collected. The other two methods determine blood loss through a calculation.

Method 2:

With this method, the EBL measurements will be based on the contents of the blood and fluid collection canisters as well as the volume reports generated by the cell saver system. To ensure blinding, final levels of fluid bags and canisters will be photographed by the study surgeon immediately after the procedure is complete. Photographs will be taken by the camera features from an iPhone 6. Photographs will be taken at a distance of two feet from the canisters and bags and such that the meniscus of the fluid is at eye-level with the lens. Photographs will be reviewed by blinded evaluators at two intervals, prior to the interim analysis and following final enrollment. Two blinded evaluators will be used for each measurement, and their measurements will be averaged for use in the final calculation.

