EBL will be calculated in the following manner: First, the total fluid volume will be calculated: The volume of the contents of all of the blood and fluid canisters used during the course of the surgical procedure will be recorded based on the photographs. To this we will add the cell saver intake fluid, taken from a report generated by the cell saver system. Next, the total irrigation volume used during surgery will be calculated. The irrigation volume will be estimated as the difference in volume of the irrigation bag at surgery cut versus surgery close. For subjects in the USBS group, the total irrigation volume will also include the difference in volume of the USBS irrigation bag at surgery cut versus surgery close. Estimated blood volume will be calculated as total fluid volume minus irrigation volume.

Method 3:

To validate the above described method 2, the study personnel will also use the same method of calculated blood loss as was used in a study by Da Cunha et al (2015).[22] The blood loss calculation from this study was adapted from the method proposed in Brechter et al (1997).[23] This method calculates blood loss through the following mathematical model:

$$EBL = [EBV * (Hb_{pre} - Hb_{post}) / Hb_{pre}] + [Donor RBC_{normalized}] + [Cell Salvage RBC_{normalized}]$$

Where:

EBV = Estimated Blood Volume = Patient Weight (kg) x 70 ml/kg

Hb_{pre} = preoperative patient Hemoglobin

Hb_{post} = postoperative Day One Patient Hemoglobin

Donor RBC_{normalized} = [donor RBC volume] x [(donor Hct) / (Hct_{pre} + Hct_{post}) / 2]

Cell Salvage RBC_{normalized} = [cell saver RBC volume] x [(cell saver Hct) / (Hct_{pre} + Hct_{post}) / 2]

Hct_{pre} = Preoperative Patient Hematocrit

Hct_{post} = Postoperative Patient Hematocrit

Patient's weight will be measured the day of surgery. Hct_{pre} and Hb_{pre} will be taken by the lead anesthesiologist prior to first incision through an ISTAT. Hct_{post} and Hb_{post} will be taken 12-18 hours after the end of the procedure through an ISTAT. Donor and cell saver Hct will be taken by the lead hematologist before bags are sent up to the OR.

f. Intraoperative Transfusion Guidelines

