Study data will be collected and managed using REDCap (Research Electronic Data Capture). REDCap is a secure web application designed to support data capture for research studies, providing user-friendly web-based case report forms, real-time data entry validation (e.g. for data types and range checks), audit trails and a de-identified data export mechanism to common statistical packages (SPSS, SAS, Stata, R/S-Plus). The system was developed by a multi-institutional consortium which includes University of Colorado–Denver and was initiated at Vanderbilt University. The database is hosted at the University of Colorado–Denver Development and Informatics Service Center (DISC), which will be used as a central location for data processing and management. REDCap data collection projects rely on a thorough study-specific data dictionary defined in an iterative self-documenting process by all members of the research team with planning assistance from the DISC. This iterative development and testing process results in a well-planned data collection strategy for individual studies. REDCap also includes a powerful tool for building and managing online surveys. The research team can create and design surveys in a web browser and engage potential respondents using a variety of notification methods. REDCap is flexible enough to be used for a variety of types of research and provides an intuitive user interface for database and survey design and data entry.

c. Potential Scientific Problems:

One potential scientific problem in this study has to do with the quantification of estimated blood loss. Past literature has revealed this measurement to be variable.[2, 25] We hope to overcome this problem by strictly adhering to the EBL collection protocol outlined above. Two research coordinators will take measurements and their measurements will be averaged for a final EBL. In this way, although the measurement is prone to misclassification, we anticipate misclassification to be non-differential. A calculated blood loss will be performed to attempt to find reproducibility between the two types of measurements and reduce potential bias. Furthermore, the research assistants, who will be performing EBL measurements and calculations, will be blinded.

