An intent to treat analysis of all randomized subjects will be performed. Descriptive statistics will be used to compare the distribution of demographics and clinical characteristics in the two groups. Baseline covariates significantly different between groups will be considered as potential confounding variables in subsequent statistical models. The primary aim of this study is to compare differences in estimated blood loss per fusion level (EBL/level) between the USBS and standard of care groups ($\theta = \theta_{USBS} - \theta_{standard\ care}$). We aim to test the null hypothesis that the difference between groups is less than or equal to 0 ($H_0: \theta \geq 0$). An independent sample t-test or multiple variable linear regression analysis, as appropriate, will be used to compare total EBL/level in the two study groups. For the secondary outcome variables, Chi-square tests will be used to compare differences in the categorical variables (the risk of adverse events, proportion of subjects meeting the intra-operative blood transfusion criteria) between the groups. Independent sample t-tests or Wilcoxon rank sum tests will be used to compare differences in the continuous variables (operative time, post-operative length of stay, and intraoperative irrigation volume).

e. Trial Monitoring/Human Subjects Research Consideration

Data Safety and Quality - All data will be collected and stored in a REDCap database. Access to the database will be restricted to investigators involved the study protocol per study personnel section of the COMIRB protocol application and/or the study delegation of duties log. Photographs obtained during surgery will be de-identified, assigned an appropriate study ID and will be stored on a secure departmental server that is managed by the IT department at Children's Hospital Colorado. The study coordinators will review data stored in the REDCap database on an ongoing basis. Potential outliers and/or biologically implausible data points will be identified and reviewed on an individual basis with the Principal Investigator.

Safety Monitoring – Based on the advice of our clinical trial study design consultant, [name], a Data Safety Monitoring Board (DSMB) will review the safety and efficacy of the study. The DMSB will consist of an orthopaedic surgeon not directly

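### Method 2 blood loss: staff described as blinded must apply a sum with a USBS-only irrigation bag, so the procedure as written reveals the arm

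*Combined protocol and SAP*

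**What the plan says.** Section II.d (Randomization and Blinding) makes evaluator blinding a safeguard for the primary outcome: "Blinded evaluators will be used to calculate the primary outcome variable of interest, estimated blood loss per level fused". Everyone else on the study team is unblinded, and this includes the surgeons. Section III.c (Potential Scientific Problems) repeats the assignment and covers both tasks: "the research assistants, who will be performing EBL measurements and calculations, will be blinded".

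Section II.e (Intraoperative Estimated Blood Loss) gives three methods. Method 1, named as the primary one, takes the EBL printed on the cell saver report. Method 2 works from collection canisters, bags and cell saver volumes. Its blinding device is photography: "To ensure blinding, final levels of fluid bags and canisters will be photographed by the study surgeon immediately after the procedure is complete". Two blinded evaluators review the photographs, before the interim analysis and after final enrollment, and their measurements are averaged. The sum is then: "Estimated blood volume will be calculated as total fluid volume minus irrigation volume". Irrigation is the change in bag volume from surgery cut to surgery close, with one arm-specific term: "For subjects in the USBS group, the total irrigation volume will also include the difference in volume of the USBS irrigation bag". Method 3 is a haemoglobin-based calculation intended to validate Method 2.

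Section III.c says that two coordinators' measurements are averaged to give the final EBL, and expects misclassification to be non-differential. Section III.e says that photographs are de-identified and given a study ID.

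**The concern.** The Method 2 sum cannot be applied without knowing whether a USBS irrigation bag was in use, and that bag exists in one arm only. The plan gives the sum to people it calls blinded and sends them photographs of the bags. It describes no dummy bag in the control arm, no cropping or mixing of images, and no separate person to total the irrigation.

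Reading a fluid level from a photograph involves judgement and is repeated over several containers per case. III.c accepts that EBL measurement is prone to error and relies partly on blinding to argue that the error does not differ by arm. If readers can tell the arm, that argument loses its support for Method 2. Averaging two readers does not remove a lean that both share.

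**Working it through.** **The text, side by side**

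| Step | Where | Assigned to | Depends on arm? |
|---|---|---|---|
| Photograph canisters and bags | II.e, Method 2 | Study surgeon (unblinded) | A USBS bag exists in one arm only |
| Read volumes from photographs | II.e, Method 2 | Two blinded evaluators | Yes, if the bag images are in the case set |
| Total the irrigation and subtract it | II.e, Method 2 | Not named there; II.d and III.c give calculation to blinded staff | Yes, extra term for USBS only |
| Method 1 EBL | II.e | Cell saver printout | No arm-specific term described |

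The second and third rows conflict with the stated blinding. A study ID removes the patient's identity, but it still groups one patient's images, so a second irrigation bag remains visible.

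**The plan's own figures**

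Inputs are SD 28 and 30 and 31 per group (II.a), and bounds Z = 2.7965 and 1.9774 (III.e).

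- Final standard error: √[(28² + 30²)/31] = √(1684/31) = 7.37 mL/level. Boundary: 1.9774 × 7.37 = 14.57, against 14.6 stated.
- Interim standard error at half information (15.5 per group): √(1684/15.5) = 10.42. Boundary: 2.7965 × 10.42 = 29.15, against 29.2 stated.
- With a true difference of 24 mL/level, power is 0.9006. With no difference, the chance of declaring USBS superior is 0.025.

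The design reproduces.

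**Illustration, only if Method 2 supplies the analysed value**

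The documents give neither a directional reading error nor the expected number of fused levels. Assume a net error e of 25 or 50 mL per case favouring USBS, and L = 8, 10 or 12 levels. Then bias b = e/L, and its share of the boundary is b/14.6. The last column is P(Z₁ > 2.7965) + P(|Z₁| ≤ 2.7965 and Z₂ > 1.9774), with means b/10.42 and b/7.37 and correlation √0.5.

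| e (mL) | L | b (mL/level) | Share of 14.6 | Chance of declaring USBS superior, no true difference |
|---|---|---|---|---|
| 0 | any | 0 | 0% | 0.025 |
| 25 | 12 | 2.08 | 14% | 0.047 |
| 25 | 10 | 2.50 | 17% | 0.052 |
| 25 | 8 | 3.12 | 21% | 0.062 |
| 50 | 12 | 4.17 | 29% | 0.081 |
| 50 | 10 | 5.00 | 34% | 0.099 |
| 50 | 8 | 6.25 | 43% | 0.132 |

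If Method 1 alone is analysed, this route adds nothing to the primary test, and the first line applies.

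**The case against.** The strongest reply is that II.e names the cell saver report as the first and primary method. That value is machine-generated and, as described, needs no photograph, no reading and no USBS bag. A reader might infer from the blinding conflict that the primary endpoint is biased; the documents do not support that. This limit stands in full. What remains is that III.c treats the two-reader average as the final EBL, and II.e schedules photograph review before the interim analysis, so the documents do not settle which value is analysed.

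Second, Method 2 is written in the passive voice and names nobody to total irrigation. Only final levels are photographed, so starting volumes must come from elsewhere, and a single irrigation total could be supplied to the evaluators. This shows that the problem can be repaired, and a reader who concluded that blinded Method 2 measurement is impossible would go too far. It does not remove the conflict, because II.d and III.c assign the calculation itself to blinded staff and II.e includes the bags among the photographs.

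Third, one might infer that the evaluators are unblinded through their job. III.c calls them coordinators, coordinators screen patients, and III.e adds: "The study coordinators will review data stored in the REDCap database on an ongoing basis". The documents do not support this. Consent precedes assignment, assignments are withheld until after enrollment, and nothing shows that the readers see allocation in REDCap. Their access is simply not specified.

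Fourth, no evidence in the documents points to a directional reading error of any given size. That is correct, and the table above is an illustration only.

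**Conclusion.** The point holds for Method 2: the procedure as written discloses the arm to the people the plan relies on as blinded. It is a defect in a stated safeguard, not evidence that results will be biased.

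Its reach to the primary test is conditional on the two-reader average being the analysed EBL. Under that condition, and under the assumed errors and levels, the bias would be 2.1 to 6.3 mL/level, and the chance of falsely declaring USBS superior would be about 0.05 to 0.13 instead of 0.025. If the cell saver value is analysed, the effect on the primary test by this route is nil; Method 2, and its comparison with Method 3, would still be affected. The change is worth making because it is cheap and the plan leans on the safeguard.

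**What to change.** 1. In II.e, separate reading from calculation. Store one image per container, cropped of device labels but with the graduations visible, under a random code that is not the study ID, and mix images across patients. Evaluators record one volume per image.
2. Lock the readings. Then apply the Method 2 sum, including starting bag volumes and the USBS bag, by script or by staff who are already unblinded.
3. Withhold the allocation and irrigation fields in REDCap from the two evaluators, and say so in II.d.
4. Reword II.d and III.c so that blinding attaches to reading volumes, not to the arm-dependent sum.
5. State consistently in II.e and III.c which method supplies the analysed EBL at the interim and final analyses.

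The same evaluators and photographs are used, and the sample size and patient care do not change. The cost is some file handling, a short script, and limited database access for two people.

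### As printed, the Method 3 red-cell terms count donor and salvaged cells at one quarter of their normalized volume because the divisor lacks a bracket

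*Combined protocol and SAP*

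**What the plan says.** Section II.e (Intraoperative Estimated Blood Loss) sets out three ways of obtaining blood loss. Method 1 is the main one: "The first and primary method is to use the estimated blood loss listed on the cell saver report". Method 2 uses canister and bag volumes. Method 3 is a calculation introduced with the purpose "To validate the above described method 2".

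Method 3 adds three terms: a hemoglobin-drop term, a normalized donor red-cell term and a normalized cell-salvage term. The hemoglobin-drop term rests on "EBV = Estimated Blood Volume = Patient Weight (kg) x 70 ml/kg". The donor term is printed as "donor RBC volume] x [(donor Hct) / (Hct_{pre} + Hct_{post}) / 2" and the salvage term as "cell saver RBC volume] x [(cell saver Hct) / (Hct_{pre} + Hct_{post}) / 2", each inside an outer pair of square brackets.

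Section III.c (Potential Scientific Problems) relies on a calculated value as a safeguard: "A calculated blood loss will be performed to attempt to find reproducibility between the two types of measurements and reduce potential bias". It does not name Method 3, but the purpose given in section II.e makes Method 3 the likely referent.

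**The concern.** A normalizing term should convert a volume of red cells at one hematocrit into the equivalent volume at the patient's hematocrit. The natural divisor is the average of the pre- and postoperative values. The printed lines contain the pieces of that average, a sum and a 2, but nothing groups them. Evaluated as written, the 2 divides a second time instead of turning the sum into a mean.

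What is at stake is the comparison of Method 3 with Method 2. The hemoglobin-drop term is correct as printed, so the error would be zero in patients given no red cells and would grow with the amount of red cells in the others. Disagreement between the methods would then track salvaged and donor volume for a purely arithmetic reason, and could be read as a weakness of the canister method.

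**Working it through.** **Notation.** V = red-cell volume, h = hematocrit of the product, a = preoperative hematocrit, b = postoperative hematocrit. The formulas come from section II.e, Method 3. The documents give no worked value to reproduce, so the patient values below are assumptions.

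**Step 1: the factor.**
- As printed: V × h / (a + b) / 2 = Vh / [2(a + b)].
- Divided by the mean: V × h / [(a + b)/2] = 2Vh / (a + b).
- Ratio, printed to mean: [1/2] / 2 = 1/4, for any V, h, a and b. The salvage line has the same structure and the same factor.

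**Step 2: identity test.** Take a = 38 and b = 28, so the mean is 33, and V = 300 mL at h = 33.
- Mean form: 300 × 33 / 33 = 300 mL, unchanged, as a normalized volume should be.
- Printed form: 300 × 33 / 66 / 2 = 75 mL.

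**Step 3: effect on the total.** Let H be the hemoglobin-drop term and R the sum of the red-cell terms in the mean form. The mean-form total is H + R and the printed total is H + R/4. The proportional shortfall is 0.75 × R / (H + R).

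Assumed patient: 50 kg, hematocrit 38 falling to 28, hemoglobin proportional to hematocrit. H = 70 × 50 × (38 − 28)/38 = 921 mL.

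| Red cells (assumed) | R, mean form (mL) | R, printed (mL) | Total, mean form (mL) | Total, printed (mL) | Shortfall |
|---|---|---|---|---|---|
| None | 0 | 0 | 921 | 921 | 0% |
| 250 mL salvaged at Hct 50 | 250 × 50/33 = 378.8 | 94.7 | 1300 | 1016 | 284 mL, 22% |
| The same plus 300 mL donor at Hct 60 | 378.8 + 300 × 60/33 = 924.2 | 231.1 | 1845 | 1152 | 693 mL, 38% |

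**Step 4: range for patients who receive one red-cell product.** The assumed grid is 40–60 kg, preoperative hematocrit 36–40, postoperative 26–30, and 200–300 mL at hematocrit 50–55 (162 combinations).
- Smallest shortfall (60 kg, 40 to 26, 200 mL at 50): H = 70 × 60 × 14/40 = 1470; R = 200 × 50/33 = 303; 0.75 × 303/1773 = 12.8%.
- Largest shortfall (40 kg, 36 to 30, 300 mL at 55): H = 70 × 40 × 6/36 = 467; R = 300 × 55/33 = 500; 0.75 × 500/967 = 38.8%.

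**Step 5: where the formula is used.** The sample size in section II.a and the stopping bounds in section III.e do not use it. The Data Analysis Plan (section III.d) specifies no between-arm test of Method 3.

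**The case against.** The strongest reply is that this is a notation slip with an obvious meaning. Two hematocrits summed and followed by a 2, in a term called normalized, read naturally as an average. Staff are also told to follow a published method that they can consult. The original page may even show a stacked fraction that text extraction flattened. No code, worked example or Method 3 result appears in the documents, so every consequence is conditional on literal coding. The analysis plan also defines no agreement statistic, threshold or action for comparing Methods 2 and 3. The two methods could in any case differ for other reasons, since Method 3 uses hemoglobin taken 12–18 hours after surgery and Method 2 measures intraoperative fluids.

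Much of this stands. The page layout should be checked, although the explicit round and square brackets in both lines look like in-line typing. The cited source is not available here and settles nothing either way. The percentages are illustrations: the grid gives every patient red cells, so it is not an average effect for this trial. It is also speculative that a discrepancy would be blamed on Method 2.

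These points limit the priority, but they do not make the printed formula right. It is an operative definition, and anyone who types it as it stands gets a wrong value with no warning.

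**Conclusion.** The concern holds. As printed, each Method 3 red-cell term is exactly one quarter of the value obtained by dividing by the mean hematocrit. That factor needs no assumption beyond ordinary order of operations. That the mean is intended is an inference, but a strong one, because only the mean leaves a volume unchanged when its hematocrit equals the patient's average.

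If coded literally, the Method 3 total is low by 0.75 times the red-cell share of the total. That is nothing in patients without donor or salvaged cells, and 13–39% across the assumed single-product grid. The damage is confined to the validation of Method 2. The correction is worth making because the error would be systematic and silent, but its priority is low.

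**What to change.** After checking the original page layout, write both lines with the divisor grouped: red-cell volume × (product hematocrit) / [(Hct_pre + Hct_post)/2].

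Confirm that the calculation code, wherever it is held, divides by the mean. One test case suffices: 300 mL at the patient's average hematocrit must return 300 mL, not 75 mL. If any Method 3 values prove to come from the literal form, recompute them before comparing Method 3 with Method 2.

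The cost is one bracket pair in each of two lines, one test run and, if needed, a recalculation from data already due to be collected. Data collection, the primary endpoint, the sample size and the stopping bounds do not change.

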Estimated blood loss/level [^]
Secondary Clinical Outcomes
Intraoperative and postoperative complications (events that cause a deviation from routine care) ^{^†‡}
Probability of meeting blood transfusion criteria (see section) ^{^†}
Procedure Time (first incision to close) [^]

Demographics/Covariates (potential confounding variables)	
Age at surgery*	BMI percentile at surgery*
Gender at surgery*	Weight (kg) at surgery*
Exposure to second hand smoke*	Preoperative Lenke Classification*
Preoperative major Cobb angle*	Preoperative hemoglobin/hematocrit*
Postoperative major Cobb angle††	Postoperative hemoglobin/hematocrit†
Intraoperative use of intrathecal narcotics^	Donor hematocrit^
Vertebral levels fused^	Intraoperative use of antifibrinolytic^

Exploratory Variables	
Unplanned return to OR††	Surgical site infection†
Procedure Time^	

* Collected preoperatively or day of surgery (before surgery)

^ Collected intraoperatively

† Collected postoperatively: short term follow-up, during initial hospital stay

‡ Collected postoperatively: long term follow-up, one year postoperative

I. Description of Population to be Enrolled:

All patients with a diagnosis of Adolescent Idiopathic Scoliosis who are scheduled for spinal fusion surgery and meet the following criteria will be eligible to participate in the study:

Inclusion Criteria:

1. 10-18 years of age
2. Diagnosis of AIS
3. Scheduled for a posterior spinal fusion (without Schwab Grade II or higher osteotomy)

Exclusion Criteria:

1. Plan for a posterior column osteotomy of Schwab Grade II or higher
2. Prior spinal surgery
3. MRI abnormalities (such as syrinx and/or chiari malformations)
4. Subjects with medical comorbidities (e.g. heart, lung, kidney disease)
5. Subjects with bleeding diatheses
6. Non-idiopathic etiology for scoliosis

II. Study Design and Research Methods

a. Power Analysis

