involved in the study, an administrator, an anesthesiologist not involved in the study, and an independent biostatistician. The DSMB will meet a minimum of three times. During the first meeting (open session), the progress of the study will be reviewed and any issues regarding safety, study feasibility, and/or protocol compliance will be discussed. This meeting will occur 1 month after the enrollment of the first study subject. The second meeting (closed) will occur after 50% of the study enrollment has been achieved. Prior to this meeting, the investigators will send a clean, unblinded dataset to the independent biostatistician that includes information regarding the primary clinical outcome of interest, estimated blood loss per level fused. This dataset will be used to determine whether any of the study stopping thresholds has been met (see Decision/Stopping Criteria below). The DSMB will meet a minimum of one additional time once 100% of the study enrollment has been achieved. Similarly, a clean, unblinded dataset will be sent to the statistician to determine whether the decision thresholds have been achieved (see Decision/Stopping Criteria below). Although unlikely, additional, emergent meetings will be scheduled as needed. The formation of the DSMB and documentation of DSMB related meetings will be done in accordance with CHCO's DSMB policy. See DSMB Charter and DSMB Reporting Form for additional information.

Safety monitoring will also be performed on ongoing basis by the PI and members of the study team. All adverse events will be submitted to the DSMB and will be reported to COMIRB within 5 business days.

[figure not shown]

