Decision/Stopping Criteria- This study will utilize a two-stage, group sequential design to monitor study progress. Under the alternative hypothesis, the two sided rejection boundaries at Stage 1 and Stage 2 were calculated according to the O'Brien-Fleming method (see Figures below). After 16 subjects per group have been enrolled, an interim analysis will be performed (Stage 1). If the standardized Z statistic representing the difference in estimated blood loss ($\hat{\theta} = \hat{\theta}_{standard\ care} - \hat{\theta}_{USBS}$) exceeds the upper or lower rejection boundary ($Z > 2.7965$ or $Z < -2.7965$), the trial will be stopped. Assuming the standard deviation of blood loss per level fused is 30 in the USBS group and 28 in the standard group, the trial will stop if $\hat{\theta} > 29.2$ mL/level or $\hat{\theta} < -29.2$ mL/level. If blood loss per level fused does not exceed the rejection bounds, the trial will continue until a total of 62 subjects have been enrolled (31 per group). At stage 2, the standardized Z statistic will be compared to the rejection bounds ($Z > 1.9774$ or $Z < -1.9774$). Assuming the standard deviation of blood loss per level fused is 30 in the USBS group and 28 in the standard group, we will conclude the USBS is superior to standard care instrument if $\hat{\theta} > 14.6$ mL/level or inferior to standard care instruments if $\hat{\theta} < -14.6$ mL/level. Sample size and stopping criteria were estimated using the RCTDesign package, R 3.1.2 (R Foundation of Statistical Computing, Vienna, Austria).

Summary of Decision Criteria - The decision criteria and potential corresponding conclusions are described in the table below.

Stage	Enrollment	Stop For Harm			Stop for Benefit		
		$\hat{\theta}_{\dagger}$	95% CI	pvalue*	$\hat{\theta}_{\dagger}$	95% CI	pvalue**
Stage 1	50%	-27.1	-42.2 to -8.55	0.005	27.1	8.55 to 42.2	0.005

Stage 2	100%	-13.9	-29.01 to 0.00	0.05	13.9	0.00 to 29.01	0.050
*Probability reject $\theta \geq 0$							
**Probability reject $\theta \leq 0$							
†Bias adjusted mean							

Figure 1. Plots of Rejection Boundaries (Red Lines) at Stage 1 and Stage 2 Relative to a Fixed Sample Design (Black Lines). 1.A Displays Rejection Boundaries on the Z Scale 1.B Displays Rejection Boundaries in Terms of EBL/level.

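### Randomisation is blocked on surgeon and gender, but the primary model is left open and its only covariate rule will not select factors that blocking has balanced; adjusting for both is a nearly free gain

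*Combined protocol and SAP*

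**What the plan says.** - **Study Design, d. Randomization and Blinding.** Allocation is 1:1 by a block scheme, and "blocks will be constructed based on surgeon and patient gender". The next sentence reads "Each surgeon will have a randomization list generated", so it is not clear whether lists are kept by surgeon only or by surgeon and gender. No block size is given.
- **Data Analysis Plan.** For the primary outcome: "An independent sample t-test or multiple variable linear regression analysis, as appropriate, will be used to compare total EBL/level in the two study groups". Nothing defines when each is appropriate. On covariates, the one criterion is: "Baseline covariates significantly different between groups will be considered as potential confounding variables in subsequent statistical models".
- **Outcome Measure(s).** The table headed "Demographics/Covariates (potential confounding variables)" includes gender but not surgeon, and does not say which variables enter the model.
- **Trial Monitoring.** The dataset for the independent biostatistician is described only as one that "includes information regarding the primary clinical outcome of interest, estimated blood loss per level fused".
- **Decision/Stopping Criteria.** Both stages use a "standardized Z statistic representing the difference in estimated blood loss", compared with 2.7965 and then 1.9774. Whether it is adjusted is not stated.

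**The concern.** When randomisation is balanced on a factor that predicts the outcome, the treatment difference varies less from trial to trial than a plain two-sample standard error assumes. A t-test that ignores the factor is then conservative and its confidence interval is too wide: the precision was bought at randomisation and is not used.

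The stated rule cannot repair this. It looks for a significant difference between arms, and blocking exists to prevent one. For the other baseline variables it reacts to chance imbalance, not to prognostic value.

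The second issue is pre-specification. The Z statistic decides whether the trial stops, yet an analyst could follow the plan with a t-test, with a regression on whatever differed at baseline, or with different models at Stage 1 and Stage 2.

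**Working it through.** **Inputs from the documents.** Difference 24 mL/level; SDs 28 (standard) and 30 (USBS); 31 per group; two-sided alpha 0.05; two looks with bounds 2.7965 and 1.9774 (Power Analysis; Decision/Stopping Criteria). Two surgeons (Subject Screening).

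**Assumed, because the documents do not give them.** R² of surgeon plus gender for EBL/level of 0, 0.1, 0.2 or 0.3, split equally between the two; surgeons 50/50; 20% male; permuted blocks of 4.

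**1. Reproducing the plan's design.** Root-mean-square SD = √((28² + 30²)/2) = 29.02. Standard error at 31 per group = 29.02 × √(2/31) = 7.37. With looks at half and full information, the O'Brien-Fleming bounds recompute to 2.7965 and 1.9774, and power is 90.06%. The Stage 2 cut-off is 1.9774 × 7.37 = 14.6 mL/level, as stated. The plan's figures therefore rest on marginal SDs, with no covariate adjustment.

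**2. Why the t-test becomes conservative.** If the factors are balanced, the true standard error is about 7.37 × √(1 − R²), while the t-test still uses about 7.37. For a single test at 1.96, the true two-sided error is 2 × [1 − Φ(1.96/√(1 − R²))]:
- R² = 0.1: 1.96/0.949 = 2.066, error 0.039
- R² = 0.2: 1.96/0.894 = 2.191, error 0.028
- R² = 0.3: 1.96/0.837 = 2.343, error 0.019

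**3. Two-stage simulation.** 62 subjects, interim at the first 32, 20,000 replicates per cell. Welch t-test against least squares on treatment, surgeon and gender, with t converted to Z through its p-value.

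| R² | Lists by | Type I error, t-test | Power, t-test | Power, adjusted |
|---|---|---|---|---|
| 0 | surgeon and gender | 0.051 | 0.891 | 0.889 |
| 0.1 | surgeon and gender | 0.039 | 0.900 | 0.918 |
| 0.2 | surgeon and gender | 0.030 | 0.911 | 0.944 |
| 0.3 | surgeon and gender | 0.019 | 0.924 | 0.969 |
| 0 | surgeon only | 0.052 | 0.892 | 0.887 |
| 0.1 | surgeon only | 0.045 | 0.895 | 0.917 |
| 0.2 | surgeon only | 0.039 | 0.903 | 0.943 |
| 0.3 | surgeon only | 0.034 | 0.907 | 0.966 |

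Type I error of the adjusted test is 0.047 to 0.052 throughout. At R² = 0.2 the mean standard error falls from 7.35 to 6.57, and 6.57/7.35 = 0.894, so the interval is about 11% narrower. With surgeons split 70/30 at R² = 0.2 (8,000 replicates), power is 0.913 against 0.946 (lists by surgeon and gender) and 0.904 against 0.948 (surgeon only).

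**4. What the stated rule selects.** The plan gives no cut-off, so p < 0.05 on a chi-square test is assumed. In 10,000 trials surgeon was selected 0 times under either reading of the lists. Gender was selected 0 times with lists by surgeon and gender, and in 5.4% of trials with lists by surgeon only.

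**5. Chance selection of other covariates.** The table marks eight variables as preoperative. For the seven other than gender, the chance that at least one differs significantly by luck is 1 − 0.95⁷ = 0.302 if they are independent, and 23% at pairwise correlation 0.5 (simulated). If the rule were applied at both looks, the selected set would differ between Stage 1 and Stage 2 in 31% to 38% of trials.

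**The case against.** The strongest reply is that nothing stated in the design fails. The t-test is valid and the 90% power holds, and the benefit of adjustment depends on an R² that the documents do not give. At R² = 0.05 the gain is under 1 point. This stands, and it is why the precision part is an improvement and not the repair of an invalid test.

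The gain is also smaller if all 72 planned enrolments supply the primary outcome, which is plausible because it is measured in theatre. A rerun at 72 gave 0.937 against 0.948 at R² = 0.1 and 0.950 against 0.972 at R² = 0.2: about 1 and 2 points. Decision/Stopping Criteria, however, sets the final look at 62.

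The mL/level cut-offs, built from the two arm SDs, suggest that an unadjusted Z was intended. That is the natural reading, but the section names no test, and the Data Analysis Plan expressly allows regression.

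Finally, the plan says only that imbalanced covariates will be considered, and the interim dataset may hold no covariates at all. The 31% to 38% figure is therefore conditional on mechanical use of the rule at both looks. That caveat is right, but discretion leaves the primary model less fixed, not more.

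**Conclusion.** The concern holds. The plan balances on surgeon and gender, commits to neither in the primary model, and offers a covariate rule that passes over what blocking has balanced. With lists by surgeon and gender that means both factors; with lists by surgeon only, surgeon is never selected and gender only by chance.

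For an assumed R² of 0.1 to 0.3, adjustment adds about 2 to 6 power points at 62 subjects, depending on R² and on how the lists are kept. If R² is zero it costs at most about half a point. The direction of the defect is benign: conservative, with no excess of false positives. The size of the gain rests on the assumed R², and the simulations also assume the surgeon split, gender mix and block size. The open model and the unsuitable selection rule rest on the text alone. The change should be made, because it is cheap and because the statistic that can stop the trial ought to be fixed in advance.

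**What to change.** 1. **Data Analysis Plan.** Replace the open choice and the baseline-significance sentence with one primary analysis: linear regression of EBL/level on treatment, surgeon and gender. The sponsor should name any further preoperative covariates in advance, on prognostic grounds. Keep the t-test as a sensitivity analysis.
2. **Decision/Stopping Criteria.** State that the Stage 1 and Stage 2 Z statistics come from the treatment coefficient of this model, with t converted to Z through its p-value, and are compared with 2.7965 and 1.9774.
3. **Design figures.** Mark the mL/level cut-offs, the decision table, and the stopping-probability and power tables as illustrations based on marginal SDs. The cut-offs are already worded as conditional on the SDs. At an assumed R² of 0.2 they would be 29.2 × √0.8 = 26.1 and 14.6 × √0.8 = 13.1.
4. **Trial Monitoring.** Include surgeon and gender in both datasets sent to the independent biostatistician.
5. **Outcome Measure(s).** Add surgeon to the covariate table.
6. **Randomization and Blinding.** State whether lists are by surgeon only or by surgeon and gender.

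The cost is wording, two dataset columns and 2 degrees of freedom. Gender is already collected, and surgeon is known from the randomisation list. Sample size and Z bounds stay as they are.
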